Up to 350 current cigarette smokers will be recruited from the community in areas of Virginia. Eligible participants will be 18 to 65 years old, smoke from 5 to 40 cigarettes per day, have a breath carbon monoxide (CO) level of at least 10 ppm at intake, and have no immediate plans to quit smoking. Females who are able to become pregnant and are: planning pregnancy, pregnant, lactating, or not willing to use contraception for the purpose of preventing pregnancy during the study will be excluded from participation. Individuals who have plans to move out of the area during the course of the experiment will also be excluded. Use of other tobacco/nicotine products will not be exclusionary. These minimally restrictive inclusion/exclusion criteria will allow for a broad range of participants and increase the generalizability to tobacco regulation of our eventual results. Participants who are not eligible may be rescreened for eligibility after at least 30 days has passed.

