Cigarette smokers will be recruited for this study. This population was chosen because the current experiment entails smoking cigarettes. Non-smokers would not be appropriate because nicotine and tobacco smoke may make individuals that do not regularly smoke feel ill. Women who can and may become pregnant (e.g., able to become pregnant and planning to become pregnant or don't use contraceptives) are excluded as the current tobacco products are investigational and risks to developing fetuses are unknown. Otherwise healthy individuals are sought to minimize any ill effects that exposure to nicotine and cigarette smoke may cause.

Section 4: Consent Process

For more information about consent process and consent forms visit the following link: <http://www.irb.vt.edu/pages/consent.htm>

If feasible, researchers are advised and may be required to obtain signed consent from each participant unless obtaining signatures leads to an increase of risk (e.g., the only record linking the subject and the research would be the consent document and the principal risk would be potential harm resulting in a breach of confidentiality). Signed consent is typically not required for low risk questionnaires (consent is implied) unless audio/video recording or an in-person interview is involved. If researchers will not be obtaining signed consent, participants must, in most cases, be supplied with consent information in a different format (e.g., in recruitment document, at the beginning of survey instrument, read to participant over the phone, information sheet physically or verbally provided to participant).

4.1 CHECK ALL OF THE FOLLOWING THAT APPLY TO THIS STUDY'S CONSENT PROCESS:

- Verbal consent will be obtained from participants
- Written/signed consent will be obtained from participants
- Consent will be implied from the return of completed questionnaire. Note: The IRB recommends providing consent information in a recruitment document or at the beginning of the questionnaire (if the study only involves implied consent, skip to Section 5 below)
- Other, describe:

4.2 PROVIDE A GENERAL DESCRIPTION OF THE PROCESS THE RESEARCH TEAM WILL USE TO OBTAIN AND MAINTAIN INFORMED CONSENT:

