The current study will take place over approximately 6 laboratory sessions at a Virginia Tech facility including the consent session (approximately 1 hour). Following informed consent, participants may also be asked to leave a baseline CO sample and urine sample (females only). The urine sample will be tested for pregnancy in females. Weight will also be measured. We have included three screening questions that ask about intentions to quit and desire to seek treatment. If a participant reports discordant answers on the intentions to quit or seek treatment questions (e.g., indicates no plans to quit but expresses an interest in treatment), we will ask a clarifying question that more directly assesses our stated exclusionary criteria of an immediate plan to quit smoking. For these participants, a question will appear that asks: "You expressed some interest in either quitting smoking or smoking cessation treatment. Do you have plans for a quit attempt in the next 30 days?" If the participant answers that s/he plans to quit, s/he will be excluded from participation after information is gathered from the assessment session but before cigarettes are provided, and provided the [name] ([name]) hotline, which can connect callers to a variety of local resources for quitting. However, the participant will be allowed to continue the experiment if there are no plans to quit in the next 30 days. All participants will complete the assessment session and only eligible participants who do not express immediate plans to quit will receive the sampling period cigarettes and return to complete the rest of the experiment. Thus, the total time commitment expected will be approximately 5 weeks.

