Assessment session (approximately 1 hour). The first lab session will be the assessment session to collect information from participants on substance use patterns and severity, as well as the results of behavioral and cognitive tasks that we think may inform or compliment the results from the main study (see appendix for examples). This may be on the same day as the consent session. All participants will complete these computerized tasks, but only eligible participants (e.g., who do not express immediate plans to quit) will be provided a 5-day supply of the experimental cigarette at the end of this session. In addition, only eligible participants will complete a demonstration of the Experimental Tobacco Marketplace, so that participants will experience the types of questions that will be asked during these sessions (see below). The experimental cigarette will be one of the following concentrations, which will be determined by random assignment initially: 0.4 mg/g, 1.4 mg/g, 2.5 mg/g, 5.6 mg/g, and 17.4 mg/g. After initial random assignment, an algorithm taking into account various demographic measures (for example, number of conventional cigarettes smoked per day, gender, nicotine yield of usual brand cigarette) will be used to assign participants to groups with the purpose of achieving balanced groups (given the between-subject design). They will be asked to use the provided cigarettes instead of their usual brand for five days. This sampling period is important to increase the generalizability of results obtained during the Experimental Tobacco Marketplace sessions and especially to allow participants to make informed decisions regarding the experimental cigarette to which they will be assigned for the remainder of the study. Participants will be informed that some of the cigarettes they will be using during the course of the study may have reduced nicotine, but will not be told the explicit concentration. If the participant is eligible to continue on through the study, the conclusion of the assessment session will occur when the participant returns the next session and reports how many experimental and non-experimental cigarettes they used during that past week. After this information is obtained, the participant will complete the first Experimental Tobacco Marketplace session.

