
The four marketplace sessions (presented in a counterbalanced order) will consist of the following conditions:

1. Price of conventional cigarettes will be manipulated with other nicotine products at a constant price
2. Price of experimental cigarettes will be manipulated with no other products available
3. Price of experimental cigarettes will be manipulated with other nicotine products at a constant price
4. A blend of 1 and 3 such that price of conventional cigarettes and experimental cigarettes will be simultaneously available (one will be manipulated while the other is held constant and vice versa) with other nicotine products at a constant price

At the last in-lab Experimental Tobacco Marketplace session participants may be recruited for an addendum to this study, which includes two additional sessions (described below). If the participant agrees and is a female, she may be retested for pregnancy at this time. Participants will only be approached and recruited contingent upon approval by the FDA Center for Tobacco Products for these additional sessions.

Post-marketplace Sampling (1 session; approximately 15-30 minutes): After at least approximately five days following the fourth marketplace session, participants may return to the laboratory for the ability to return any unused experimenter provided products for a refund and report the number of tobacco products used since the previous session. During this session, all participants, regardless of assigned investigational cigarette concentration, will be provided five-days' worth each of the "high" (17.4 mg/g) and "low" (0.4 mg/g) investigational cigarette. In addition to the "Investigational Tobacco Product" label, these cigarettes will be labeled with arbitrary codes e.g., "A" and "B" (randomized across participants as to which concentration the code reflects); for subsequent tasks, participants will be told that cigarette "C" refers to the investigational cigarette they were assigned to at the onset of the study. Participants will be told to use only these cigarettes for the following five days.

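### Experiment 2 can dispense addendum cigarettes without a current pregnancy test, and its form omits Experiment 1's withdrawal and pregnancy-outcome rules

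*Combined protocol and SAP*

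**What the plan says.** In the Experiment 2 form, section 3.1 lists the women to be excluded: "Females who are able to become pregnant and are: planning pregnancy, pregnant, lactating, or not willing to use contraception". Section 3.4 gives the reason: the products are investigational and "risks to developing fetuses are unknown".

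Section 5.1 sets out testing and supply in this order:

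- After consent, "participants may also be asked to leave a baseline CO sample and urine sample (females only"; any urine sample is tested for pregnancy.
- Eligible participants "will be provided a 5-day supply of the experimental cigarette at the end of this session", meaning the assessment session.
- Four marketplace sessions follow. At the last one, participants may be recruited to an addendum, and of a woman who agrees the form says: "If the participant agrees and is a female, she may be retested for pregnancy at this time". It adds: "Participants will only be approached and recruited contingent upon approval by the FDA Center for Tobacco Products for these additional sessions".
- The next visit comes later: "After at least approximately five days following the fourth marketplace session, participants may return to the laboratory". At that visit, "all participants, regardless of assigned investigational cigarette concentration, will be provided five-days' worth each of the" 17.4 and 0.4 mg/g cigarettes, to be used over the next five days.

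Section 6.2 names pregnancy as a contraindication to screen for. For medical problems or adverse events during the study it provides a general assessment of whether the participant should stay in or keep using study products. It says nothing specific about a pregnancy that arises on study.

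The Experiment 1 form does. Its section 5.1 withdraws a woman who tests positive and follows her by phone until the outcome is known. Its section 6.2 applies withdrawal and follow-up to anyone who becomes pregnant during the study.

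**The concern.** The exclusion rests on unknown fetal risk, but the form carries that reasoning no further than entry. In the addendum the test is permissive and the supply is not. The two are also separated in time, so even a retest that is done does not describe the woman's status on the day she takes the cigarettes home.

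The second gap concerns what happens once a pregnancy is known. The same group, using the same five nicotine concentrations, wrote withdrawal and outcome rules for Experiment 1, where the study cigarettes are smoked in the laboratory. It left them out of Experiment 2, where they are taken home. Staff following the Experiment 2 form would have to work out for themselves that supply should stop, and nothing tells them to record how the pregnancy ended. For a product whose fetal risk is called unknown, that outcome is the information most worth keeping.

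**Working it through.** The plan states no figure on this point, so there is none to reproduce. The check is a count of visit intervals and a comparison of the two forms.

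**Age of the last test at addendum dispensing**

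Inputs, all from Experiment 2 section 5.1: a five-day sampling period before the first marketplace session; at least about five days after each marketplace session; dispensing at least about five days after the fourth; a stated total commitment of about five weeks. Assumption: consent, baseline test and assessment fall on one day (day 0), which the form allows. If the assessment comes later, the gap grows by that delay.

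- Intervals from baseline to dispensing: assessment to session 1, three between sessions 1 and 4, and session 4 to dispensing, so 1 + 3 + 1 = 5.
- Minimum spacing: 5 × 5 = 25 days. Sessions fall on days 5, 10, 15 and 20; dispensing is on day 25.
- Stated schedule: 5 weeks × 7 = 35 days. If day 35 is the fourth session, dispensing is on day 35 + 5 = 40. If the five weeks already include the return visit, it is on day 35.
- If the optional retest is done at session 4: 25 − 20 = 5 days old at dispensing, at least.

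**The two forms side by side**

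| Item | Experiment 1 | Experiment 2 |
|---|---|---|
| Baseline urine sample | Worded as *may* (5.1) | Worded as *may* (5.1) |
| Later test | Required, but only if more than seven purchase sessions are needed and participation reaches week 6 (5.1) | Optional, on agreeing to the addendum (5.1) |
| Action on a positive later test | Withdrawal (5.1) | Not stated |
| Pregnancy arising on study | Withdrawal (6.2) | Not stated; general assessment only (6.2) |
| Pregnancy outcome | Followed by phone (5.1, 6.2) | Not stated |
| Where study cigarettes are used | Laboratory booth | Away from the laboratory |

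The other safeguards in the Experiment 2 form are the contraception requirement at entry (3.1), FDA approval before anyone is approached for the addendum (5.1), and reporting of serious adverse events to the FDA (1.4). None states a retest, a withdrawal rule or outcome follow-up.

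**The case against.** The best defence is that the form contains the substance even where the wording is thin. Pregnancy is an exclusion, section 6.2 calls it a contraindication, and a test placed at addendum enrolment makes little sense unless a positive result bars entry. The optional wording may only reflect that some women cannot become pregnant. The baseline sample uses the same word, so it is selective to treat one test as done and the other as skippable. Experiment 1 also has no retest before its sixth week. And the consent pages and the FDA addendum submission are not available here.

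Much of this stands. Withdrawal, and refusal of addendum supply after a positive test, can fairly be inferred. The shared wording cuts the other way, though: if the baseline sample is also optional on its face, the form guarantees less testing, not more. No reading of the exclusions or of the general assessment yields outcome follow-up. Nor does any reading bring the retest to the dispensing day.

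Three stronger inferences are tempting and are not supported:

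- *Experiment 2 tests less often than Experiment 1.* Experiment 1's retest applies only to over-running participants, so it is no benchmark for test frequency. The comparison holds only for the withdrawal and outcome rules.
- *The study adds fetal exposure that can be counted in cigarettes.* The form gives no cigarette numbers, marketplace purchases vary with price and income, and unused products can be returned. The participants already smoke and are told to use the study cigarettes in place of their own.
- *Women who become pregnant will be kept on study products.* The form provides an assessment that could stop supply; what is missing is an explicit rule. Documents not seen may contain one.

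**Conclusion.** The concern holds in a limited form, as a cheap improvement to participant safety. Followed as written, Experiment 2 section 5.1 permits take-home 0.4 and 17.4 mg/g cigarettes to be given to a woman able to become pregnant about 25 days or more after her last test, or about 35 to 40 days on the stated schedule. If the optional retest is done, the result is still at least about five days old. The intervals assume that the baseline test was done and fell on the same day as the assessment. Separately, the form has no explicit pregnancy-withdrawal rule and no provision at all for following a pregnancy to its outcome.

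The documents give neither the number of women nor the number of addendum entrants, so the number affected cannot be stated. No estimate, power figure or analysis is touched. If the consent form or operating procedures already hold these rules, the remaining task is to bring this form into line with them; its closing statement requires that it be followed and kept current.

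**What to change.** Two edits to the Experiment 2 form:

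1. Section 5.1, addendum: replace the optional retest with a required one. Females able to become pregnant are tested at the post-marketplace sampling session, and addendum cigarettes are dispensed only after a negative result that day.
2. Section 6.2: carry over Experiment 1's rules. A participant who becomes pregnant during the study is withdrawn, receives no further investigational cigarettes, and is followed by phone until the pregnancy outcome is established.

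The cost is amendment wording, one urine test per eligible woman entering the addendum (already foreseen, now mandatory and moved to the dispensing visit), and a few calls. All four marketplace sessions are complete by then, so a positive result at that visit loses addendum data only. Unused products can already be returned at the same visit.

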7.1 DOES THE RESEARCH INVOLVE MICROWAVES/X-RAYS, OR GENERAL ANESTHESIA OR SEDATION?

No
 Yes

7.2 DO RESEARCH ACTIVITIES INVOLVE PRISONERS, PREGNANT WOMEN, FETUSES, HUMAN IN VITRO FERTILIZATION, OR MENTALLY DISABLED PERSONS?

No, go to question 7.3
 Yes, answer questions within table

IF YES

This research involves:

Prisoners
 Pregnant women Fetuses Human in vitro fertilization
 Mentally disabled persons

7.3 DOES THIS STUDY INVOLVE MORE THAN MINIMAL RISK TO STUDY PARTICIPANTS?

Minimal risk means that the probability and magnitude of harm or discomfort anticipated in the research are not greater in and of themselves than those ordinarily encountered in daily activities or during the performance of routine physical or psychological examinations or tests. Examples of research involving greater than minimal risk include collecting data about abuse or illegal activities. Note: if the project qualifies for Exempt review (<http://www.irb.vt.edu/pages/categories.htm>), it will not need to go to the Full Board.

No
 Yes

IF YOU ANSWERED "YES" TO ANY ONE OF THE ABOVE QUESTIONS, 7.1, 7.2, OR 7.3, THE BOARD MAY REVIEW THE PROJECT'S APPLICATION MATERIALS AT ITS MONTHLY MEETING. VIEW THE FOLLOWING LINK FOR DEADLINES AND ADDITIONAL INFORMATION: <http://www.irb.vt.edu/pages/deadlines.htm>

Section 8: Confidentiality / Anonymity

For more information about confidentiality and anonymity visit the following link: <http://www.irb.vt.edu/pages/confidentiality.htm>

8.1 WILL PERSONALLY IDENTIFYING STUDY RESULTS OR DATA BE RELEASED TO ANYONE OUTSIDE OF THE RESEARCH TEAM?

For example – to the funding agency or outside data analyst, or participants identified in publications with individual consent

No

Yes, to whom will identifying data be released? **Participant's identifying information (e.g., name, address, phone number) may be released to the VTCRI administrative offices and the VT Controller's office in order to process the petty cash reimbursements for participant payments.**

8.2 WILL ANY STUDY FILES CONTAIN PARTICIPANT IDENTIFYING INFORMATION (E.G., NAME, CONTACT INFORMATION, VIDEO/AUDIO RECORDINGS)?

Note: if collecting signatures on a consent form, select "Yes."

No, go to question 8.3

Yes, answer questions within table

IF YES

Describe if/how the study will utilize study codes: Using only ID numbers and initials and keeping all data in locked offices will protect confidentiality. Computer databases will have coded identifiers and all computers will be password protected.

If applicable, where will the key [i.e., linked code and identifying information document (for instance, John Doe = study ID 001)] be stored and who will have access? Master files linking subject names to study ID numbers will be accessible only to trained study team members delegated this access by the PI.

Note: the key should be stored separately from subjects' completed data documents and accessibility should be limited.

The IRB strongly suggests and may require that all data documents (e.g., questionnaire responses, interview responses, etc.) do not include or request identifying information (e.g., name, contact information, etc.) from participants. If you need to link subjects' identifying information to subjects' data documents, use a study ID/code on all data documents.

8.3 WHERE WILL DATA BE STORED?

Examples of data - questionnaire, interview responses, downloaded online survey data, observation recordings, biological samples

All data and participant binders will be stored in a safe place to protect confidential participant information. Safe places will include locked filing cabinets or locked rooms accessible only to study personnel. The full names of participants will not be listed on the outside of binders to protect confidentiality of study participants.

Electronic data will be saved in secure, limited access shared drives on password-protected computers accessible only to the research team.

8.4 WHO WILL HAVE ACCESS TO STUDY DATA?

Access to study data will be limited to study personnel who have completed the Virginia Tech IRB Human Subjects Tutorial and who have been delegated the responsibilities of data collection, management, or analyses by the PI.

8.5 DESCRIBE THE PLANS FOR RETAINING OR DESTROYING THE STUDY DATA

Data collected from this study will be retained and destroyed in accordance with the center's policy that requires a 3-year retention period following final publication of the data.

8.6 DOES THIS STUDY REQUEST INFORMATION FROM PARTICIPANTS REGARDING ILLEGAL BEHAVIOR?

No, go to question 9.1

Yes, answer questions within table

IF YES

Does the study plan to obtain a Certificate of Confidentiality?

No

Yes (Note: participants must be fully informed of the conditions of the Certificate of Confidentiality within the consent process and form)

For more information about Certificates of Confidentiality, visit the following link:

<http://www.irb.vt.edu/pages/coc.htm>

Section 9: Compensation

For more information about compensating subjects, visit the following link: <http://www.irb.vt.edu/pages/compensation.htm>

9.1 WILL SUBJECTS BE COMPENSATED FOR THEIR PARTICIPATION?

No, go to question 10.1

Yes, answer questions within table

IF YES

What is the amount of compensation? Compensation for participation will be as follows:

\$20.00 for completion of informed consent

\$40.00 for the assessment session (for those who are eligible to go on during the study, compensation will be provided in the following way: \$10 for the initial assessment session and \$30 for returning and reporting the products used during the sampling period)

\$20.00 compensation for time spent completing each of the Experimental Tobacco Marketplace sessions

\$75.00 bonus for completing all aspects of the experiment

Participants may also receive the following compensation if they are recruited for and agree to participate in the addendum:

\$10 for the post-marketplace sampling session

\$20 for the post-sampling session

Combined, the subjects could be compensated approximately up to \$215 - \$245 (if subjects complete the addendum) by completing all aspects of the experiment.

In addition, participants will receive between approximately \$6.25 and \$50.00 each purchase session to purchase tobacco/nicotine products. The amount each participant receives will be proportional to his/her real-world cigarette expenditure. These amounts will not be advertised as, or considered, compensation.

To allow for payments that are both convenient and rapidly available, we may pay participants with reloadable prepaid cards through Greenphire ClinCard (www.greenphire.com), an FDIC-insured payment provider that specializes in clinical trial stipend payments that comply with IRB privacy regulations and considerations. At the beginning of the study, the participant will receive a prepaid MasterCard debit card that can be used anywhere that accepts MasterCard. As payments are earned in the course of the study, additional funds will be added to the account

for that participant. Funds are immediately available when added and participants can check their balance as desired. This system will allow frequent, immediately available payments. Payments may also be made via check, however remote debit card payments will be used most often.

Will compensation be prorated?

Yes, please describe: **Subjects will be compensated based on what study procedures he/she has completed.**

No, explain why and clarify whether subjects will receive full compensation if they withdraw from the study?

Unless justified by the researcher, compensation should be prorated based on duration of study participation. Payment must not be contingent upon completion of study procedures. In other words, even if the subject decides to withdraw from the study, he/she should be compensated, at least partially, based on what study procedures he/she has completed.

Section 10: Audio / Video Recording

For more information about audio/video recording participants, visit the following link: <http://www.irb.vt.edu/pages/recordings.htm>

